#### \*\* Severity Index

The maximum intensity of an AE during a day should be graded according to the definitions below and recorded in details as indicated on the CRF. If the intensity of an AE changes over a number of days, then separate entries should be made having distinct onset dates.

1. Mild: AEs are usually transient, requiring no special treatment, and do not interfere with patient's daily activities.
2. Moderate: AEs typically introduce a low level of inconvenience or concern to the patient and may interfere with daily activities, but are usually ameliorated by simple therapeutic measures.
3. Severe: AEs interrupt a patient's usual daily activity and traditionally require systemic drug therapy or other treatment.

#### **8.3.2 Sponsor-Investigator reporting: Notifying the FDA**

The sponsor-investigator will report to the FDA all serious, unexpected and suspected adverse reactions according to the required IND Safety Reporting timelines, formats and requirements.

Unexpected fatal or life threatening suspected adverse reactions where there is evidence to suggest a causal relationship between the study drug/placebo and the adverse event, will be reported as a serious suspected adverse reaction. This will be reported to the FDA on FDA Form 3500A, no later than 7 calendar days after the sponsor-investigator's initial receipt of the information about the event.

Other unexpected serious suspected adverse reactions where there is evidence to suggest a causal relationship between the study drug/placebo and the adverse event, will be reported as a serious suspected adverse reaction. This will be reported to the FDA on FDA Form 3500A, no later than 15 calendar days after the sponsor-investigator's initial receipt of the information about the event.

Any clinically important increase in the rate of serious suspected adverse reactions over those listed in the protocol or product insert will be reported as a serious suspected adverse reaction.

This will be reported to the FDA on FDA Form 3500A no later than 15 calendar days after the sponsor-investigator's initial receipt of the information about the event.

Findings from other studies in human or animals that suggest a significant risk in humans exposed to the drug will be reported. This will be reported to the FDA on FDA Form 3500A, no later than 15 calendar days after the sponsor-investigators initial receipt of the information about the event.

#### **8.4 Unmasking/Unblinding Procedures**

The study statistician will be responsible for revealing the treatment assignments (i.e. unblinding) when necessary. Since no interim analysis is planned for this study, unblinding will occur only when 1) a serious adverse event is observed and the treatment assignment must be made known and/or 2) at the conclusion of the study at the time of data analysis to evaluate treatment safety and preliminary efficacy.

#### **8.5 Stopping Rules**

The stopping rules specified below are based on the knowledge available at study development. We note that the Adverse Event Stopping Rule may be adjusted at any time during the conduct of the trial and in consideration of newly acquired information regarding the adverse event profile of the treatment under investigation. The study team may choose to suspend accrual because of unexpected adverse event profiles that have not crossed the specified rule below.

Accrual will be temporarily suspended to this study if at any time we observe events considered at least possibly related to study treatment (i.e. an adverse event with attribute specified as "possible", "probable", or "definite") that satisfy either of the following:

- If the first two patients or 3 consecutive at any point experience a SAE deemed related to study drug as defined in section 8.3.
- If a patient death considered related to the agent occurs.

The protocol will be reviewed by the study team. It will not be re-opened without proper protocol modification. If no modifications are possible then the study will close and be permanently stopped.

If a subject experiences an adverse event assessed as  $\geq$  Grade 2 in the System Organ Classes (SOCs) of Cardiac Disorders and Blood and Lymphatic System disorders, or  $\geq$  Grade 3 for all other SOCs, according to Common Terminology Criteria for Adverse Events (CTCAE v4), the subject will not receive additional doses. Subjects should remain in the study and be followed until the adverse event resolves or stabilizes.

We note that we will review grade 4, and 5 adverse events deemed "unrelated" or "unlikely to be related" to verify their attribution and to monitor the emergence of a previously unrecognized treatment-related adverse event.

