#### 4.3 Subject Recruitment, Enrollment and Screening

Prior to discussing study enrollment with the patient, principal investigator, [name] and/or [name], will discuss with study coordinator to ensure that that target enrollment has not yet been met.. Subjects will be recruited at Mayo Clinic Department of Dermatology and Division of Plastic Surgery in Rochester, Minnesota.

At the time of patient enrollment in the trial the following must be verified:

1. IRB approval of the trial and open enrollment status with both Mayo Clinic and clinicaltrials.gov.
2. Open place on the enrollment log (confirmation from the PI and study coordinator).
3. Patient is willing and able to travel to the Mayo Clinic, Rochester for all tests, treatment and follow up required in the protocol.

At the time of patient enrollment the following will be confirmed and documented:

1. A signed consent form.

2. The existence of a signed authorization for use and disclosure of protected health information.
3. A completed inclusion/exclusion enrollment checklist.

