### **5.7.3 Dispensing of Study Drug**

Per Mayo Clinic Research Pharmacy policy, pharmacists and/or pharmacy technicians under the supervision of a pharmacist will prepare and dispense investigational products per study protocol. Lot numbers and expiration dates of commercial supplies utilized in the preparation of investigational products such as syringes, needles, IV bags, tubing, diluents, and standard of care products are not tracked.

Single dose containers will help to ensure accurate and consistent dosing across all patients participating in the trial. Approximately 1.8 mL (0.06 oz) of TP and placebo PCCA PP will be topically applied to the designated scar region. The randomized treatment group (TP versus PCCA PP) will be assigned to subjects in a double-blinded manner by the research pharmacist; details in Section 5.5. Patients will be educated on topical drug application during the pre-operative clinic visit. The patient will be instructed to apply enough study drug to thoroughly cover the area to be treated. It is not necessary to use the entire dose for each treatment application, but a minimum of at least half should be used. The patient will be asked to administer a sample product in the presence of a study coordinator to verify their application technique and amount. Once the patient demonstrates understanding and skill, the patient may personally administer the remaining treatments during the trial.

Single dose containers will be distributed to patients at visit 2 and visit 3. Each treatment set will contain 8 active and 8 placebo containers to be applied every 48 hours. Any unused containers will be returned by the patient at their next follow-up visit (return bag for used containers will be provided). Randomized treatment label will contain instructions for site-specific application. Patients are held accountable for keeping track of dispensed drug at all times. If a dose of the drug is lost due to unforeseen circumstances, a single replacement may be available.

Regular study drug reconciliation will be performed to document drug assigned, drug dispensed, drug returns, and drug remaining. This reconciliation will be logged on the drug reconciliation form, and signed and dated by the study team.

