### 7.3 Subject Population(s) for Analysis

This study will include only subjects who completed ALL study-related procedures and follow up.

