**8.3 Reporting of Serious Adverse Events and Unanticipated Problems**

When an adverse event has been identified, the study team will take appropriate action necessary to protect the study participant and then complete the Study Adverse Event Worksheet and log. The sponsor-investigator will evaluate the event(s) and determine the necessary follow-up and reporting required.

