## **10 Study Monitoring, Auditing, and Inspecting**

### **10.1 Study Monitoring Plan**

This study will be monitored on a routine basis during the conduct of the trial. The Mayo Clinic Office of Research Regulatory Support will provide clinical monitoring for the trial as a service for the sponsor-investigator. Clinical trial monitoring requires review of the study data generated throughout the duration of the study to ensure the validity and integrity of the data along with the protection of human research subjects. This will assist sponsor-investigators in complying with Food and Drug Administration regulations.

The investigator will allocate adequate time for such monitoring activities. The Investigator will also ensure that the monitor or other compliance or quality assurance reviewer is given access to all the study-related documents and study related facilities (e.g. pharmacy, diagnostic laboratory, etc.), and has adequate space to conduct the monitoring visit.

Data and safety monitoring provides a clinical investigation with a system for appropriate oversight and attention to the protection of human subjects by the investigator, research team, or an independent reviewer. A Data and Safety Monitoring Plan is a quality assurance plan for a research study. A written Data and Safety Monitoring Plan (DSMP) prospectively identifies and documents monitoring activities intended to protect the safety of the subjects, the validity of the data and the integrity of the research study. The DSMP may also identify when to terminate a subject's participation (i.e. individual stopping rules) and/or the appropriate termination of a study (i.e. study stopping rules).

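### The study-level stopping rule in section 8.5 expressly suspends accrual only; no stated rule holds dosing or dispensing for other patients already on treatment

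*Combined protocol and SAP*

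**What the plan says.** Section 8.5 (Stopping Rules) works at two levels.

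- **Study level.** The triggers are a drug-related serious adverse event (SAE) in each of the first two patients or in any three consecutive patients, or one related death. Attribution of possible, probable or definite counts. The response is "Accrual will be temporarily suspended to this study if at any time we observe events considered at least possibly related to study treatment". The study team then reviews the protocol. Of that stage the section says "It will not be re-opened without proper protocol modification", and the study closes permanently if no modification is possible. No time limit is set for the review. The optional step for a worrying profile short of the triggers is also suspension of accrual.
- **Subject level.** After a CTCAE event of Grade 2 or higher (cardiac, or blood and lymphatic) or Grade 3 or higher (any other class), "the subject will not receive additional doses". This covers the subject who had the event.

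Each patient applies active gel to one end of the scar and base alone to the other (section 1.6.5), at home, every 48 hours for 4 weeks. Eight active and eight placebo containers are dispensed on the day of surgery and again at week 2 (section 5.5). The primary goal is safety (section 2).

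**The concern.** A stopping rule has to protect two groups: people not yet enrolled and people already exposed. As written, 8.5 expressly protects only the first. The within-subject design makes this sharper. There is no placebo-only patient, so everyone on treatment when a trigger is met is using pentamidine. Unblinding under 8.4 would show only which end of the scar received it.

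The two levels of the rule also sit oddly together. One Grade 3 event ends that subject's own dosing, but a drug-related death does not, in terms, require anyone else to stop.

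Section 7.1 calls this a first-in-human study. Section 5.1 gives a terminal half-life of 2 to 4 weeks and warns of accumulation with repeated dosing. The documents do not state systemic uptake from the gel, so this is a reason for caution and not evidence of harm.

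**Working it through.** **1. Is a hold stated anywhere?** The plan gives no figure on this point, so the first check is textual.

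| Section | What it provides | A stated hold for other patients? |
|---|---|---|
| 8.5, study level | Accrual suspended, review, possible permanent closure | No; patients on treatment are not mentioned |
| 8.5, subject level | "the subject will not receive additional doses" | No; affected subject only |
| 4.4.1 | Withdrawal for safety reasons | No; discretionary, per subject |
| 5.5 | Principal investigator signs the drug order | No; allows supply to be withheld but does not require it |
| 8.3 | "the study team will take appropriate action necessary to protect the study participant" | No; concerns the participant with the event |
| 8.3.1, 8.3.2 | Deadlines for reports to the IRB and FDA | No; reporting only |
| 8.6, 10.1 | Investigator oversight and a monitoring plan; "The DSMP may also identify when to terminate" | Not in the text available |

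**2. Applications left per patient.** Surgery is day 0, the first dose is at 24 hours and then every 48 hours (section 5.2). With 14 applications (section 5.3; section 3.1 gives 14 to 16), the dose days are 1, 3, …, 27.

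- After the day-1 dose: 14 − 1 = 13 left.
- Before a week-2 visit on day 14 (days 3, 5, 7, 9, 11, 13): 6, from containers already at home.
- After it (days 15, 17, …, 27): 7, from the second supply. Eight containers are dispensed and seven are used by day 13. If the spare covers day 15, the split is 7 and 6.
- Between contacts on days 1, 7, 14, 21 and 28: 3, 3, 4 and 3 applications.
- In any 7 days starting from days 1 to 20: 3 or 4. This is also what fits inside the 7-day FDA reporting limit in 8.3.2.

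**3. Amount applied to skin.** I assume that 2% means 20 mg/mL. Section 5.7.3 says "It is not necessary to use the entire dose for each treatment application, but a minimum of at least half should be used", so one application is 0.9 to 1.8 mL, or 18 to 36 mg.

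- 13 applications: 13 × 18 = 234 mg to 13 × 36 = 468 mg.
- The 6 at home: 108 to 216 mg. The 7 on a new order: 126 to 252 mg.

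These are amounts applied, not systemic doses.

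**4. Who else is exposed?** The accrual rate is not stated, and I found no required interval between patients. As an illustration, assume equal spacing *s* and that the first trigger is met on patient 2's day *e*. Patient *k* is then on day *e* − (*k* − 2)*s*. Doses left are the dose days after that day. Patients not yet at day 1 are not counted.

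| Patient 2's day | s = 7 days | s = 14 days | s = 28 days |
|---|---|---|---|
| 14 | 10 | 0 | 0 |
| 21 | 7 + 10 = 17 | 10 | 0 |
| 28 | 3 + 7 + 10 = 20 | 7 | 0 |
| 30 | 2 + 6 + 9 + 13 = 30 | 6 + 13 = 19 | 13 |

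The last row matters because 8.5 applies at any time and section 8.1 runs the reporting period to 3 months after the last administration. At 4-week spacing, patient 2's day 30 is patient 3's day 30 − 28 = 2, with 13 doses left.

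**The case against.** Four points can be made for the plan.

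- **The wording of 8.5.** In "It will not be re-opened without proper protocol modification", the grammatical subject is the protocol, and the next step is closure of the whole study. A reader could fairly take all protocol activity to be suspended. Against this, accrual is the only thing the section says is suspended, and section 4.3 uses the same vocabulary for enrollment: "IRB approval of the trial and open enrollment status with both Mayo Clinic and clinicaltrials.gov". That supports the narrower reading without settling it. The ambiguity stands, and a stopping rule should not depend on it.
- **Discretion.** This is one site with ten subjects. The principal investigator oversees safety, signs drug orders and signs off reported adverse events within 24 hours, and 8.5 lets the adverse-event rule be adjusted at any time. This is substantial. A refused order could block the week-2 supply. It does not reach containers already at home, and none of it is mandatory.
- **An unseen plan.** Section 8.6 requires a site data and safety monitoring plan, which may contain a hold. It is not in the documents, and 10.1 is only permissive on the point.
- **The figures are conditional.** The probability of a trigger is not estimated, spacing is assumed, and the three-consecutive trigger is not quantified. This is right: the table shows what could happen, not an expected exposure.

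A reader might infer that the protocol requires dosing to continue after a related death, or that the trial has no hold at all. The documents support neither, given the discretion and the unseen plan. The opposite inference, that slow accrual removes the problem, also fails: 4-week spacing gives zero only if events after day 28 are ignored. For the same reason, an average over on-treatment days would not describe the exposure.

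**Conclusion.** The point holds as a gap in the stated rule. When a study-level trigger is met, 8.5 expressly suspends accrual only, its re-opening sentence is ambiguous, and no section available states a hold on application or dispensing for other patients on treatment.

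The per-patient size is up to 13 of 14 applications, assuming the 14-dose schedule and a patient just past day 1. The number of other patients affected cannot be fixed from the documents. It may be none or several, and 4-week spacing does not rule it out.

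This is a cheap improvement that should be made. Confidence is medium, because discretion or the monitoring plan may already cover it in practice.

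**What to change.** Amend 8.5 along these lines:

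> If either trigger is met, enrollment, application of study drug and dispensing of study drug are all suspended for every subject on treatment. Subjects are contacted promptly and told to stop using containers they hold, and the week-2 supply is withheld. Neither enrollment nor dosing resumes until the review is complete and any required modification is approved. Missed applications are not made up. Scheduled safety follow-up continues.

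Add a clause to 7.3 keeping held subjects in the safety analysis. That section now reads "This study will include only subjects who completed ALL study-related procedures and follow up", which could remove them.

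The change needs a few sentences and no extra patients or procedures. It has three costs:

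- **Interrupted courses.** Some 4-week treatments would be broken or cut short.
- **False alarms.** Possible attribution counts, and the SAE list in 8.1 includes hospitalization and tissue necrosis, either of which could follow the surgery itself.
- **Lost efficacy data.** Section 7.3 does not say whether missed applications count as incomplete procedures. If they do, held subjects drop out of the efficacy analysis, and the SAE patients stopped under 8.5 may too. For a two-sided paired t-test at 0.05 with 80% power, the detectable difference, in SDs of the within-patient differences, is 1.00 at n = 10, 1.07 at n = 9 (one held), 1.27 at n = 7 (three held) and 1.68 at n = 5 (three held and two SAE patients). This is before any effect of suspended accrual.

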#### **5.5 Packaging**

The research pharmacy will order 300 mg Pentam vials via Rochester Methodist Campus (RMC) pharmacy purchasing specialists from APP Pharmaceuticals. Pentam vials will be stored within the research pharmacy (20-25°C) and sent to the compounding pharmacy when the study drug order is placed. The study drug order will be initiated by the study coordinator following patient consent, and as needed based on the date of surgery and 2 week postoperative visit. The Principle Investigator will sign the order which is then forwarded to the research pharmacy to be filled. For production, 300 mg Pentam (pentamidine isethionate) product will be compounded into non-aqueous silicone base vehicle (Pracasil™-Plus (PCCA #30-4655; PCCA PP) for 2% topical gel.

The compounding pharmacy will prepare the single containers for storage and dispensation by the research pharmacy. The research pharmacy will dispense a specified quantity of containers according to patient-specific prescription signed by IRB-authorized prescriber. The study coordinator will pick up the prescription from the research pharmacy and provide to the patient on visit 2 (day of surgery) and visit 3 (2 week postop clinic visit). Each dispensation will contain 8 active and 8 placebo containers to be applied every 48 hours; all containers (used and unused) will be returned by the patient at their next follow-up visits.

The research pharmacy will perform randomization schema to determine treatment to dispense for proximal versus distal scar areas. The research pharmacy maintains electronic records of investigational medication inventory and dispensation activities for the study; thus randomization will be performed for enrolled patients electronically via Medidata and Scientific Data Management System (SDMS). All Mayo Clinic Research Pharmacy staff members are required by policy to complete the Mayo Clinic Human Subject Protection and CITI Good Clinical Practice Training once every 3 years. The designated Research Pharmacy staff member assigned primary responsibilities for the study reviews all sponsor documents and prepares instruction sheets outlining storage, handling, electronic order entry and preparation of all investigational agents as indicated in the study protocol and pharmacy manual.

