### 5.6 Masking/Blinding of Study

This is a double-blinded study; subjects and clinical investigators (physicians, nurse practitioners and study delegates) will be blinded to the treatment. Study treatments (either TP or control PCCA PP base) will be packaged at the Mayo Clinic Compounding Pharmacy as described above. Compounding pharmacists will be aware of the study drug and will provide an unidentified label (please see example in Section 5.5) with lot number only for each treatment application. At the completion of the study, investigators will be unmasked following data interpretation and statistical analysis.

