## Adverse Event Reporting Period

For this study, the study treatment follow-up period is defined as 3 months following the last administration of study treatment.

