## 8.6 Medical Monitoring

It is the responsibility of the Principal Investigator to oversee the safety of the study at his/her site. This safety monitoring will include careful assessment and appropriate reporting of adverse events as noted above, as well as the construction and implementation of a site data and safety-monitoring plan (see section 10 “Study Monitoring, Auditing, and Inspecting”). Medical monitoring will include a regular assessment of the number and type of serious adverse events.

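### Apart from a related death, the only mandatory accrual-suspension trigger in Section 8.5 depends on patient order, so scattered non-fatal related SAEs are left to discretion; a cumulative count of three is a cheap improvement, with a gain that overlapping enrolment may make small

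*Combined protocol and SAP*

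**What the plan says.** Section 8.5 requires temporary suspension of accrual, for events rated possibly, probably or definitely related, in two cases. One is a related death. The other is "If the first two patients or 3 consecutive at any point experience a SAE deemed related to study drug". The section does not say what makes patients consecutive.

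Below that threshold, action is optional: "The study team may choose to suspend accrual because of unexpected adverse event profiles that have not crossed the specified rule below". The section also lets the rule be adjusted at any time. After a mandatory suspension the study team reviews the protocol: "It will not be re-opened without proper protocol modification". If no modification is possible, the study closes permanently.

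A separate criterion based on CTCAE grade stops dosing for the affected subject only. Section 8.6 adds: "Medical monitoring will include a regular assessment of the number and type of serious adverse events". Section 10.1 says that a data and safety monitoring plan may contain study stopping rules, but states none. Sections 8.3.1 and 8.3.2 set IRB and FDA reporting duties.

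Ten subjects are planned (Section 3.2).

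**The concern.** Safety is the primary objective, and Section 7.1 describes the study as the first in humans. Every patient receives active gel on one end of the excised scar under one fixed regimen (Sections 5.2 and 5.3), with no dose escalation that would make neighbouring patients more alike than distant ones. A third related SAE is therefore evidence of harm wherever it falls in the sequence. The written rule counts it only if the three patients are adjacent, or if two of them are the first two enrolled.

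At stake are the patients not yet enrolled when the third event becomes known. Whether accrual pauses for them would, in most orderings, rest on judgement and not on a stated number.

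**Working it through.** **Inputs from the protocol.** n = 10 (Section 3.2). The written rule fires if patients 1 and 2 are both affected, or if any three consecutive patients are (Section 8.5). The protocol gives no operating characteristics for the rule, so there is no figure to reproduce first.

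**Assumptions.** Consecutive means enrolment order. Events are non-fatal, since a related death triggers suspension by itself. Each ordering has equal weight. The comparator keeps the first-two trigger and adds a third affected patient in any position.

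**Three affected.** Orderings: C(10,3) = 120. The rule fires in 8 sets of the form {1, 2, x} plus 8 runs of three, minus 1 overlap ({1, 2, 3}) = 15. Silent: 120 − 15 = 105 (87.5%).

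Orderings with all three among the first nine: C(9,3) = 84, of which the rule fires in 7 + 7 − 1 = 13. So 84 − 13 = 71 silent orderings reach the third affected patient by patient 9. In the other 105 − 71 = 34 the third is patient 10, when no enrolment is left to spare.

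**Four affected.** Orderings: C(10,4) = 210. Sets containing patients 1 and 2: C(8,2) = 28. Sets containing a run of at least three: 49. Both: 7. Fires: 28 + 49 − 7 = 70. Silent: 140. The third of four affected patients always falls by patient 9, so the cumulative count acts by then in all 140.

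**More affected (enumeration).** Silent in 96 of 252 with 5, 26 of 210 with 6, and 1 of 120 with 7 (only patients 2, 5 and 8 unaffected). With 8 or more the rule always fires.

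**Lag.** Suppose L further patients enrol before the third event is known. The cumulative count then spares at least one enrolment only if (position of third affected patient) + L ≤ 9.

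| L | 0 | 1 | 2 | 3 | 4 | 5 | 6 |
|---|---|---|---|---|---|---|---|
| 3 affected (of 105 silent) | 71 | 45 | 26 | 13 | 5 | 1 | 0 |
| 4 affected (of 140 silent) | 140 | 120 | 87 | 52 | 23 | 5 | 0 |

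The protocol does not state enrolment spacing. The Study Summary gives 3 months for both the whole study and one subject's participation; read literally, that means nearly concurrent enrolment. Section 8.1 adds that "the study treatment follow-up period is defined as 3 months following the last administration of study treatment".

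**Assumed SAE rates.** The protocol gives none. With independent patients at rate p, P(suspension) = Σ N(k) p^k (1 − p)^(10−k), where N(k) is the number of orderings with k affected in which the rule fires. At p = 0.10 the cumulative rule gives P(at least 3) = 0.0702, plus 0.1² × 0.9⁸ = 0.0043 for patients 1 and 2 alone, or 0.0745.

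| Assumed rate | P(suspension), written vs cumulative | Mean enrolments avoided, no lag | Mean avoided, lag of 3 |
|---|---|---|---|
| 5% | 0.3% vs 1.3% | 0.02 vs 0.04 | 0.013 vs 0.015 |
| 10% | 1.6% vs 7.4% | 0.10 vs 0.20 | 0.055 vs 0.070 |
| 20% | 8.3% vs 32.9% | 0.45 vs 0.97 | 0.238 vs 0.326 |

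At a lag of 5 the gain falls to about 0.0001, 0.001 and 0.006 enrolments. At 10%, the rise in suspensions is 7.45 − 1.63 = 5.82 points. Of this, (7.45 − 5.78) − (1.63 − 1.54) = 1.58 points are pauses at patient 10, which spare nobody (5.78 and 1.54 are the probabilities of suspension by patient 9).

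**Dominance.** Across all 1,024 outcome sequences, the cumulative rule fires whenever the written rule does, at the same patient or earlier.

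**The case against.** The strongest reply is that scattered events are already covered. Section 3.4 expects no severe events, so three related SAEs fit closely the unexpected profiles for which the team may suspend. The rule can be changed at any time, SAE numbers are reviewed regularly, and Section 8.3.2 requires FDA reporting of a clinically important rise in the rate of serious suspected reactions within 15 days. A reader might infer that the protocol has no answer to scattered SAEs; the documents do not support that. What stands is narrower: none of these safeguards, as written, forces a pause at a stated number of affected patients. The monitoring plan may, but it was not among the documents reviewed.

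Second, order can carry information. Drug is ordered per patient (Section 5.5) and labelled "with lot number only for each treatment application", so a run may point to a bad lot. This is a fair reason to act on a run, but the cumulative rule still fires on every run of three.

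Third, the benefit may be slight and the cost real. A rating of possible covers events that other causes could explain (Section 8.3.1, Relationship Index), every patient has surgery, and hospitalization and tissue necrosis count as serious (Section 8.1). SAEs that are really surgical could accumulate to three. With one fixed regimen there may be little to modify, so a pause could end the study. This stands in full and limits the strength of the recommendation.

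Fourth, the protocol names no unacceptable SAE rate, so neither 8.3% nor 32.9% at a 20% rate can be called wrong. That also stands: this is a design choice, not an error.

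**Conclusion.** The point holds as a suggestion worth considering. Apart from a related death, the only mandatory trigger is order-dependent. It is silent in 105 of 120 orderings with 3 of 10 affected, 140 of 210 with 4 and 96 of 252 with 5, and it can be silent with 7. These counts rest only on reading consecutive as enrolment order and weighting orderings equally.

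It is tempting to read the 71 of 105 as the protection that patients would gain. The documents do not support that: it is a best case that needs each outcome to be known before the next enrolment. At lags of 1 to 6 patients the count falls to 45, 26, 13, 5, 1 and 0, and the only timeline in the protocol suggests that overlap may be heavy, although it may be loosely drafted. The expected gain is material only if the SAE rate is high and overlap is limited. The rate-based figures also assume independent patients, which a lot effect would break.

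**What to change.** In the first bullet of Section 8.5, keep the first-two trigger and state that it means enrolment order. Replace the run of three with *any 3 patients cumulatively, consecutive or not, with an SAE at least possibly related to study drug*. Keep the death trigger, and put the same rule in the data and safety monitoring plan. If the sponsor prefers the run rule, define consecutive and say why scattered events are left to discretion.

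The drafting cost is an amendment of one bullet. The operating cost is more pauses: 1.3% against 0.3%, 7.4% against 1.6%, and 32.9% against 8.3% at assumed SAE rates of 5, 10 and 20%. Some would follow surgical events rated only possible, and some would come at patient 10 and spare nobody. Each needs a protocol modification before re-opening, and if none is possible the study closes for good.
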